### **Analysis**

- Results will be process and analyzed as mean +/- standard deviation for continuous variables, and percentage for categorical variable.
- Positive predicted value, negative predicted value, sensitivity, specificity of both white light and NBI system will be calculated

- Statistical difference will be compared by chi-square test. P<0.05 was set as statistically significant
- Statistical analysis will be carried out with SPSS version 13

**Ethic issue/ Major point in consent form**

- Prolonged the endoscopy examination time

**Target Patient number:**

- New case: 50-70

Title:

Using narrow-band imaging (NBI) technique to detect post-radiotherapy mucosal residual nasopharyngeal carcinoma (NPC)

Principle Investigator

[name] [name],

Statistical Analysis plan

1. Post-RT NP NBI vessel pattern were analyzed
2. Vessel pattern will be divided into NBI suspicious group and NBI non suspicious group
3. 2x2 table of suspicious/ non-suspicious group vs no residual disease / have residual disease will be obtained
4. Chi-square test will be performed, p-value will be contained
5. Sensitivity, specificity, positive predicted value, negative predicted value of using NBI to detect mucosal residual NPC will be calculated

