## **Objective**

1. To identify the vessel pattern of those confirmed NPC case using NBI system
2. To identify the endoscopy features of post-radiotherapy mucosal residual nasopharyngeal carcinoma using NBI system
3. To establish the positive predicted value, negative predicted value, sensitivity and specificity of using both normal white light (WL) endoscopy and NBI system for detecting mucosal residual NPC

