### **Method**

- 1 A New ENT NBI clinic **is established and held** on every Friday pm (preferably) and Wednesday am (in case the patient is not available on Friday pm session or Friday is a public holiday)
- 2 Newly biopsy confirmed NPC patient
  - 2.1 Department of ENT: All biopsy confirmed NPC patients will be called back to the NBI clinic. They will be assessed by [name] and a complete ENT examination would be performed. Patient will undergo endoscopy examination (both WL + NBI), endoscopy image will be stored in the ePR system, consent forms will be signed and, baseline pure tone audiogram will be arranged. Patients will also be referred to oncology department.
  - 2.2 Department of Oncology: All new biopsy confirmed NPC patients **will be referred to ENT NBI clinic**. They will be assessed by [name] and a complete ENT examination would be performed. Patient will undergo endoscopy examination (both WL + NBI), endoscopy image will be stored in the ePR system, consent forms will be signed and, baseline pure tone audiogram will be arranged.
- 3 All patients will be followed up by both oncology and ENT department (**in ENT general clinic**) together regularly and look for chemo-radiation complication and hearing impairment.
- 4 At post-radiotherapy (2nd weeks) follow up in oncology department
  - 4.1 An appointment at post-radiotherapy 8th weeks will be arranged for the ENT NBI clinic (preferably on Friday pm) to perform nasopharynx biopsy
  - 4.2 An appointment at post-radiotherapy 10th weeks will be arranged for the oncology clinic to review biopsy result
- 5 At post-radiotherapy 8th weeks NBI clinic: The patient will undergo endoscopy examination (both WL and NBI) and nasopharyngeal biopsy will be taken. All the images will be saved in ePR. The consultation note template will be as same as the oncology endoscopy session template.
- 6 Biopsy results will be reviewed by oncology colleagues at the post-radiotherapy 10th weeks clinic

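### The plan gives no confidence interval for sensitivity, specificity, PPV or NPV, although estimating these is the third objective and sensitivity rests on the residual cases alone

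*SAP*

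**What the plan says.** The third item under Objective in the Protocol, on finding residual disease in the mucosa, reads "To establish the positive predicted value, negative predicted value, sensitivity and specificity of using both normal white light (WL) endoscopy and NBI system". The Protocol's Analysis section follows this with "Positive predicted value, negative predicted value, sensitivity, specificity of both white light and NBI system will be calculated" and then "Statistical difference will be compared by chi-square test. P<0.05 was set as statistically significant". The only measure of spread it names is the standard deviation, for continuous variables. Categorical variables are to be given as percentages.

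The SAP has five numbered items. Item 2 is "Vessel pattern will be divided into NBI suspicious group and NBI non suspicious group". Item 3 cross-tabulates those two groups against presence or absence of residual disease. Item 4 is "Chi-square test will be performed, p-value will be contained". Item 5 is "Sensitivity, specificity, positive predicted value, negative predicted value of using NBI to detect mucosal residual NPC will be calculated".

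Neither document mentions a confidence interval, a standard error or a target precision for an accuracy measure. The target number in the Protocol is 50-70 new cases, with no derivation.

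**The concern.** An accuracy objective is an estimation objective, and an estimate without a statement of its uncertainty answers it only in part. This matters most for sensitivity, whose denominator is the number of patients with residual disease and not the number enrolled. An observed sensitivity of 100% could come from 3 patients or from 21, and the plan requires nothing that would tell these apart.

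The one inferential result in the SAP does not fill the gap. Its null hypothesis is that NBI class and residual disease are unrelated. A small p-value rejects that, but it says nothing about whether sensitivity is near 40% or near 95%.

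**Working it through.** **The plan's own figure.** The 50-70 target cannot be reproduced, because no residual rate, expected accuracy, precision or power is given.

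**Inputs.** From the documents: 50-70 patients (Protocol, Target Patient number) and a significance level of 0.05 with sidedness not stated (Protocol, Analysis). I take a two-sided 95% interval as its counterpart. Assumed, because the documents are silent: a residual rate of 5-30%, and all observed counts below.

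**Denominator for sensitivity.** Residual cases = n × rate.
- Low end: 50 × 0.05 = 2.5, taken as 3.
- High end: 70 × 0.30 = 21.
- Between: 60 × 0.10 = 6 and 70 × 0.20 = 14.

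**Exact (Clopper-Pearson) limits for x detected of n.** Lower = 2.5% quantile of Beta(x, n − x + 1); upper = 97.5% quantile of Beta(x + 1, n − x). When x = n the upper limit is 1 and the lower limit is 0.025^(1/n); for 3/3 it is 0.025^(1/3) = 0.292.

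| Residual cases | All detected | Not all detected |
|---|---|---|
| 3 | 3/3 = 100% (29-100%) | |
| 6 | 6/6 = 100% (54-100%) | 5/6 = 83% (36-100%) |
| 14 | 14/14 = 100% (77-100%) | 11/14 = 79% (49-95%) |
| 21 | 21/21 = 100% (84-100%) | 17/21 = 81% (58-95%) |

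Even at 21 cases, the 17/21 interval spans 95 − 58 = 37 points.

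**What the association p-value shows.** Take an assumed table for 60 patients: 5 residual cases NBI-suspicious, 1 residual case not suspicious, 8 non-residual suspicious, 46 non-residual not suspicious.
- Uncorrected chi-square = n(ad − bc)² / (product of the margins) = 60 × (5 × 46 − 1 × 8)² / (6 × 54 × 13 × 47) = 60 × 49,284 / 197,964 = 14.94, p = 0.0001.
- The smallest expected count is 6 × 13 / 60 = 1.3, so the uncorrected test is doubtful here. Fisher's exact test gives p = 0.0012.

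Exact 95% intervals from the same table:
- Sensitivity 5/6 = 83% (36-100%)
- Specificity 46/54 = 85% (73-93%)
- PPV 5/13 = 38% (14-68%)
- NPV 46/47 = 98% (89-100%)

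Under either test the association is clear, yet the data are compatible with a sensitivity anywhere from 36% to nearly 100%. Specificity, with 54 patients behind it, has an interval of 93 − 73 = 20 points.

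**Does the result depend on the interval method?** The Wilson limits are [p + z²/2n ± z√(p(1 − p)/n + z²/4n²)] / (1 + z²/n). For 5/6 with z = 1.96: centre (0.8333 + 0.3201)/1.6403 = 0.703, half-width 1.96 × √(0.02315 + 0.02668)/1.6403 = 0.267, so 44-97%. This is narrower than the exact interval but still 53 points wide.

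**The case against.** Four objections deserve weight.

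*The harm is recoverable.* Leaving out intervals biases no estimate and changes no data collected. SAP item 3 produces the NBI table, from which a reader could compute intervals if it is published. This stands, and it limits how serious the point is. It does not help for white light, because the SAP defines no white-light groups and no white-light table.

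*Nothing says that accuracy will be judged by the p-value.* A reader might infer that the plan intends to claim good accuracy from a significant chi-square. The documents do not support that: they state no success criterion, no accuracy threshold and no rule linking the p-value to a conclusion. The point is only that the plan has no statement of precision and that the p-value cannot serve as one.

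*Every width above rests on assumed counts.* A reader might infer that the study is bound to be too imprecise. The documents give no residual rate, so this cannot be said. The absence of intervals is documentary; their width is illustrative.

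*Clopper-Pearson is conservative.* This is correct, and it is not the only acceptable interval, as the Wilson result shows. What is needed is a named method, fixed in advance, that behaves acceptably with few cases and at an observed 0% or 100%.

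Two neighbouring matters are separate points. The Protocol's Analysis section does not say what its chi-square compares, and nothing is claimed here about that test. A comparison of NBI with white light would be paired, since both are done in each patient at the week-8 visit ("The patient will undergo endoscopy examination (both WL and NBI) and nasopharyngeal biopsy will be taken"), but this point does not depend on it.

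**Conclusion.** The point holds as an omission: both documents plan point estimates of four accuracy measures and a p-value, with no interval for any of them. The SAP's test of association does not convey the precision of the estimates. With 50-70 patients and an assumed residual rate of 5-30%, sensitivity would rest on about 3-21 patients, with exact 95% intervals from 29-100% (3/3) to 58-95% (17/21). These sizes rest on the assumed rate and counts; the omission and the remedy do not. If residual cases turn out to be many, the intervals will show adequate precision.

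The change should be made, but the omission does not invalidate the study: the estimates are unaffected and the data remain usable.

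**What to change.** In SAP item 5 and in the Protocol's Analysis section, write: *Sensitivity, specificity, PPV and NPV of NBI and of white light will each be reported as numerator/denominator with a two-sided 95% confidence interval (Clopper-Pearson), and statements on accuracy will be based on these intervals. The chi-square test of NBI class against residual disease will be reported as a test of association only.* Wilson may be named instead; the choice should be fixed before analysis. Each measure takes its own denominator: residual, non-residual, test-positive or test-negative patients.

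The Protocol already plans white-light accuracy, so SAP items 2-3 need the matching suspicious/non-suspicious grouping for white light and its 2x2 table.

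**Cost.** For NBI, one sentence in each document and minutes of analysis, with no extra patients or procedures. White light costs more, because it needs a written classification. If none was recorded at the visit, it would have to be read from the stored images ("All the images will be saved in ePR"), without knowledge of the biopsy result.

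**Downside.** The results will look less precise, and the intervals disclose a small number of residual cases without curing it. They also do not supply the missing justification for the target of 50-70.
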